7.0 DOSE DELAYS / DOSE MODIFICATIONS

Patients will be monitored closely for toxicity and dose delays will be implemented where clinically necessary as per the ASCO guideline: Management of Immune-Related Adverse Events in Patients Treated with Immune Checkpoint Inhibitors. (For more information, please see: <https://ascopubs.org/doi/full/10.1200/JCO.2017.77.6385>) No dose modifications are permitted.)

7.1 Dose Delay Criteria

CPI administration should be withheld for the following:

1. Any grade 3 drug-related AE
2. Any drug-related AE requiring the initiation of prednisone >10 mg per day (or equivalent steroid dose).
3. Any AE, laboratory abnormality, or intercurrent illness which, in the judgment of the investigator, warrants delaying the dose of study medication.

7.2 Criteria to Resume Treatment

Subjects may resume treatment when the following criteria are met

1. Subjects may resume treatment when any drug-related laboratory or clinically AE revert to grade 1 or less.
2. Any AE that in the judgment of the investigator has sufficiently resolved.
3. Prednisone < 10mg per day (or equivalent steroid dose).

7.3 Discontinuation Criteria

Treatment should be permanently discontinued for the following:

1. Any grade 4 drug-related AE warrants permanent discontinuation, unless it is a reversible endocrinopathy.
2. Any adverse event, laboratory abnormality, or intercurrent illness which, in the judgment of the Investigator, presents a substantial clinical risk to the subject with continued CPI dosing

8.0 ADVERSE EVENTS AND POTENTIAL RISKS

8.1 Adverse Event Definition

An Adverse Event (AE) is defined as any new untoward medical occurrence or worsening of a preexisting medical condition in a clinical investigation subject administered an investigational (medicinal) product and that does not necessarily have a causal relationship with this treatment. An AE can therefore be any unfavorable and unintended sign (such as an abnormal laboratory finding), symptom, or disease temporally associated with the use of investigational product, whether or not considered related to the investigational product.

The causal relationship to study drug is determined by a physician and should be used to assess all adverse events (AE). The causal relationship can be one of the following:

Related: There is a reasonable causal relationship between study drug administration and the AE.

Not related: There is not a reasonable causal relationship between study drug administration and the AE.

The term "reasonable causal relationship" means there is evidence to suggest a causal relationship.

Adverse events can be spontaneously reported or elicited during open-ended questioning, examination, or evaluation of a subject. (In order to prevent reporting bias, subjects should not be questioned regarding the specific occurrence of one or more AEs.)

8.2 Serious Adverse Events Definition

A Serious Adverse Event (SAE) is any untoward medical occurrence that at any dose:

- results in death
- is life-threatening (defined as an event in which the subject was at risk of death at the time of the event; it does not refer to an event which hypothetically might have caused death if it were more severe)
- requires inpatient hospitalization or causes prolongation of existing hospitalization (see NOTE below)
- results in persistent or significant disability/incapacity
- is a congenital anomaly/birth defect
- is an important medical event (defined as a medical event(s) that may not be immediately life-threatening or result in death or hospitalization but, based upon appropriate medical and scientific judgment, may jeopardize the subject or may require intervention [eg, medical, surgical] to prevent one of the other serious outcomes listed in the definition above.) Examples of such events include, but are not limited to, intensive treatment in an emergency room or at home for allergic bronchospasm; blood dyscrasias or convulsions that do not result in hospitalization.)
- Potential drug induced liver injury (DILI) is also considered an important medical event.
- Suspected transmission of an infectious agent (eg, pathogenic or nonpathogenic) via the study drug is an SAE.
- Although pregnancy, overdose, and cancer are not always serious by regulatory definition, these events must be handled as SAEs.

8.3 Non-Serious Adverse Events Definition

- A non-serious adverse event is an AE not classified as serious.

8.4 Adverse Event Evaluation

The collection of Grade ≥ 2 AE and SAE information should begin at initiation of study drug. All non-serious adverse events (not only those deemed to be treatment-related) should be collected continuously during the treatment period and for a minimum of 30 days following the last dose of study treatment or until next treatment is initiated, whichever comes first.

Baseline physical and laboratory Grade ≥ 2 AEs should be followed to resolution or stabilization or reported as SAEs if they become serious. Follow-up is also required for non-serious AEs that cause interruption or discontinuation of study drug and for those present at the end of study treatment as appropriate.

A laboratory test abnormality considered clinically relevant (e.g., causing the subject to withdraw from the study, requiring treatment or causing apparent clinical manifestations, result in a delay or dose modification of study treatment, or judged relevant by the investigator), should be reported as an adverse event.

The investigator or sub-investigator (treating physician if applicable) will provide the following for all adverse events (both serious and non-serious):

- Event term (as per CTCAE)
- Description of the event
- Date of onset and resolution
- Expectedness of the toxicity
- Grade of toxicity
- Attribution of relatedness to the investigational agent- (this must be assigned by an investigator, sub-investigator, or treating physician)
- Action taken as a result of the event, including but not limited to; no changes, dose interrupted, reduced, discontinued, etc. or action taken with regard to the event, i.e. no action, received conmed or other intervention, etc.
- Outcome of event

Descriptions and **grading scales** found in the NCI Common Terminology Criteria for Adverse Events (CTCAE) version 5.0 will be utilized for AE reporting. (for more information, please see

https://ctep.cancer.gov/protocolDevelopment/electronic_applications/ctc.htm#ctc_50)

An **expected adverse event** is an event previously known or anticipated to result from participation in the research study or any underlying disease, disorder, or condition of the subject. The event is usually listed in the Investigator Brochure, consent form or research protocol.

An **unexpected adverse event** is an adverse event not previously known or anticipated to result from the research study or any underlying disease, disorder, or condition of the subject.

Attribution is the relationship between an adverse event or serious adverse event and the study drug. Attribution will be assigned as follows:

- Definite – The AE is clearly related to the study drug.
- Probable – The AE is likely related to the study drug.
- Possible – The AE may be related to the study drug.
- Unlikely – The AE is doubtfully related to the study drug.
- Unrelated – The AE is clearly NOT related to the study drug.

Protocol must specify if attribution is required for individual components of the treatment regimen or the treatment regimen as a whole.

8.5 Reporting Procedures for Serious Adverse Events and OnCore®

Following the subject's written consent to participate in the study, all SAEs, whether related or not related to study drug, must be collected, including those thought to be

associated with protocol-specified procedures. All SAEs must be collected that occur within 30 days of discontinuation of dosing or until next treatment is initiated

All SAEs must be collected that occur during the screening period. If applicable, SAEs must be collected that relate to any protocol-specified procedure (eg, a follow-up skin biopsy). All SAEs should be monitored until they are resolved or are clearly determined to be due to a subject's stable or chronic condition or intercurrent illness(es). The investigator should report any SAE that occurs after these time periods that is believed to be related to study drug or protocol-specified procedure.

SAEs will be recorded on the FDA Form 3500A (MedWatch) according to the reporting guidelines in section 8.5.

8.6 Serious Adverse Events and OnCore®

All SAEs will be entered into OnCore.

8.7 Reporting Procedures for Serious Adverse Events and OnCore®

It is the responsibility of each site PI to ensure that ALL SAEs occurring on this trial (internal or external) are reported to the Case Comprehensive Cancer Center's Data and Safety Toxicity Committee. This submission is simultaneous with their submission to the sponsor and/or other regulatory bodies.

The sponsor-investigator is responsible for submitting an annual report to the DSTC as per CCCC Data and Safety Monitoring Plan.

8.8 Data and Safety Monitoring Plan

This protocol will adhere to the policies of the Case Comprehensive Cancer Center Data and Safety Monitoring Plan in accordance with NCI guidelines.

9.0 PHARMACEUTICAL INFORMATION

9.1 Pembrolizumab Product Information

Product description and dosage form	Potency	Primary Packaging (volume)/Label type	Appearance	Storage condition (per label)
Pembrolizumab Solution for Injection	100 mg/Vial (25 mg/mL)	4 mL type 1 flint glass vials	Clear to opalescent, colorless to pale yellow liquid. May contain particles	Stores at 2 to 8 degrees Celsius (36 to 46 degrees Fahrenheit) and protected from light and freezing.

Please refer to FDA package insert for further details.

(https://www.accessdata.fda.gov/drugsatfda_docs/label/2016/125514s012lbl.pdf)

Pembrolizumab will be given every three weeks at a dose of 200 mg to be administered as a 30 minute IV infusion. Pembrolizumab can also be given every six weeks at a dose of 400 mg to be administered as a 30 minute IV infusion. Decision on pembrolizumab dose will be based on provider discretion.

Subjects may be dosed every 21 days (or 42 days for 400mg dose) +/- 3 days from the previous dose of drug. There are no premedications recommended for pembrolizumab on the first cycle. Subjects should be carefully monitored for infusion reactions during pembrolizumab administration. If an acute infusion reaction is noted, subjects should be managed according to Section 6.1.

9.2 Atezolizumab Product information

Product description and dosage form	Potency	Primary Packaging (volume)/Label type	Appearance	Storage condition (per label)
Atezolizumab Solution for injection	1200 mg/Vial (60 mg/mL)	20 mL type 1 flint glass vials	Clear to opalescent, colorless to pale yellow liquid. May contain particles	Stores at 2 to 8 degrees Celsius (36 to 46 degrees Fahrenheit) and protected from light and freezing.

Please refer to FDA package insert for further details.

(https://www.accessdata.fda.gov/drugsatfda_docs/label/2018/761034s010lbl.pdf)

Atezolizumab will be given every three weeks at a dose of 1200 mg to be administered as a 60 minute IV infusion. If the first infusion is tolerated, all subsequent infusions may be delivered over 30 minutes.

Subjects may be dosed every 21 days +/- 3 days from the previous dose of drug. There are no premedications recommended for atezolizumab on the first cycle. Subjects should be carefully monitored for infusion reactions during atezolizumab administration. If an acute infusion reaction is noted, subjects should be managed according to Protocol Section 6.1.

9.3 Durvalumab Product Information

Product description and dosage form	Potency	Primary Packaging (volume)/Label type	Appearance	Storage condition (per label)
Durvalumab Solution for Injection	500 mg/vial (50 mg/mL)	10 mL type 1 flint glass vials	Clear to opalescent, colorless to pale yellow liquid. May contain particles	Stores at 2 to 8 degrees Celsius (36 to 46 degrees Fahrenheit) and protected
	120 mg/vial (50 mg/mL)	2.4 mL type 1 flint glass vials		

				from light and freezing. 4 hours at room temperature up to 25 degree Celsius (77 degree Fahrenheit)
--	--	--	--	--

Please refer to FDA package insert for further details.

(https://www.accessdata.fda.gov/drugsatfda_docs/label/2017/761069s000lbl.pdf)

Durvalumab will be given every 2 weeks at a dose of 10 mg/kg to be administered as a 60 minute IV infusion.

Subjects may be dosed every 14 days +/- 2 days from the previous dose of drug. There are no premedications recommended for durvalumab on the first cycle. Subjects should be carefully monitored for infusion reactions during durvalumab administration. If an acute infusion reaction is noted, subjects should be managed according to Protocol Section 6.1.

9.4 Nivolumab Product Information

Product description and dosage form	Potency	Primary Packaging (volume)/Label type	Appearance	Storage condition (per label)
Nivolumab Solution for Injection	100 mg/Vial (10 mg/mL)	10 mL type 1 flint glass vials	Clear to opalescent, colorless to pale yellow liquid. May contain particles	Stores at 2 to 8 degrees Celsius (36 to 46 degrees Fahrenheit) and protected from light and freezing.
	40 mg/vial (10 mg/mL)	4 mL type 1 flint glass vials		
	240 mg/vial (10 mg/mL)	24 mL type 1 flint glass vials		

Please refer to FDA package insert for further details.

(https://www.accessdata.fda.gov/drugsatfda_docs/label/2018/125554s058lbl.pdf)

Nivolumab will be given every four weeks at a dose of 480mg to be administered as a 30 minute IV infusion.

Subjects may be dosed every 28 days +/- 3 days from the previous dose of drug. There are no premedications recommended for nivolumab on the first cycle. Subjects should be carefully monitored for infusion reactions during nivolumab administration. If an acute infusion reaction is noted, subjects should be managed according to Protocol Section 6.1.

9.5 Avelumab Product Information

Product description and dosage form	Potency	Primary Packaging (volume)/Label type	Appearance	Storage condition (per label)
Avelumab Solution for Injection	200 mg/Vial (20 mg/mL)	10 mL type 1 flint glass vials	Clear to opalescent, colorless to pale yellow liquid. May contain particles	Stores at 2 to 8 degrees Celsius (36 to 46 degrees Fahrenheit) and protected from light and freezing.

Please refer to FDA package insert for further details.

(https://www.accessdata.fda.gov/drugsatfda_docs/label/2019/761049s006lbl.pdf)

Avelumab will be given every 2 weeks at a dose of 800 mg to be administered as a 60 minute IV infusion.

Subjects may be dosed every 14 days +/- 2 days from the previous dose of drug. Patients will need to be premedicated with acetaminophen and an antihistamine for the first 4 infusions and subsequently as needed. Subjects should be carefully monitored for infusion reactions during avelumab administration. If an acute infusion reaction is noted, subjects should be managed according to Protocol Section 6.1.

10.0 CORRELATIVE STUDIES

Please reference Section 1.4 for Background and Rationale for Correlative Studies

10.1 Blood Correlatives

At the time of imaging patients will also undergo blood draws for immunomodulatory cells. Whole blood (2 10 ml Sodium Heparin vacutainer tubes) will be collected for all time points by a member of the research team and delivered to the lab of [name] [name] (Cleveland Clinic Lerner Research Institute) for processing. Levels of cytokines associated with the suppressive function of MDSCs and Tregs (IL-1B, IL-10, IL-6, TGF-beta) and/or associated with anti-tumor activity of T cells (IFN- gamma, TNF-alpha) will be measured by ELISA in the plasma and correlated with levels of MDSC subtypes (PMN(granulocytic) (CD33+CD15+CD14- HLADR-), immature (CD33+CD15-CD14- HLADR-) and monocytic (CD33+CD14+CD15-HLADR-)) and Tregs (CD4+CD25+FOXP3+) by flow cytometry. Plasma will also be frozen and stored for future analyses.

10.2 Tissue Correlatives

Biopsies are recommended at specific time points to investigate the genomic and immunologic markers that are associated with response or resistance to therapy. Regarding biopsy timing, a biopsy is recommended at any time during cycle 1 (for PR and SD patients) and within 3 weeks of any other time period at which a PD or PR is

achieved in any patient (unless not feasible or unsafe per investigator discretion). Fresh biopsy specimens will be sent to the Lab of [name] for nucleic acid isolation for gene expression analyses. In the event that archival tissue is only available nucleic acid will be isolated from formalin fixed tissue. A minimum of 3 unstained slides, up to 6 months prior to enrollment are allowed. Samples will be sent to the lab of [name] within 30 days of enrollment. Nucleic acid will be stored in a designated freezer at -80°C.

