1.4 Background and rationale of correlative studies

Immunotherapy functions to modulate the immune microenvironment. Myeloid derived suppressor cells (MDSC), CD8⁺ and CD4⁺ T cells, regulatory T cells (Tregs), T cell receptor (TCR) repertoire, among others are important contributors both to the

function of and resistance to targeted therapy and immunotherapy.³³⁻³⁶ For example, in melanoma, patients with higher numbers of circulating T_{reg} cells and T_{eff} cells after CPI therapy were predictive of treatment responses.^{37,38} CPI therapy was also associated with changes to the TCR repertoire, which is crucial to T cell functioning.³⁹ Additionally, in breast and colon cancer, MDSC levels have correlated with treatment response, disease progression, and clinical outcomes.³⁴ Specifically in urothelial carcinoma, MDSCs in peripheral blood have been correlated with pathology and response to CPI therapies.^{40,41}

The tumor microenvironment as well as the peripheral blood are dynamic and subject to change based on changes in tumor burden and therapy. There is a lack of prospective data demonstrating correlations between changes in peripheral blood and changes in the tumor microenvironment. The goal of this study is to generate a hypothesis that changes in the type and behavior of immunomodulatory cells in the peripheral blood will reflect tumor burden and that such changes will impact tumor burden while on CPI therapy. The presence of a biomarker (or composite biomarker score) to identify patients likely to benefit from CPI will help prospectively select patients for therapy. Likewise, the development of biomarkers to determine which patients are likely to tolerate extended breaks from therapy without compromising efficacy, will minimize toxicity for select patients.

Another point of interest would be to evaluate the rate at which the PD-1 receptor occupancy on peripheral blood circulating T cells changes over time with CPI suspension. Previous studies have shown PD-1 receptors can remain occupied for >10 months despite non-detectable levels in the blood.³¹ This is potentially a reason why patients have “durable” responses and slow resolving toxicities to immunotherapy even after discontinuation. Understanding the pharmacodynamics of anti-PD-1/anti-PD-L1 therapy on PD-1 receptor occupancy is crucial in developing a dose suspension schedule.

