2.3 Correlative Objective(s)

- Tissue: Investigate the genomic and immunologic markers of response and resistance to therapy.
- Blood: Investigate the immunomodulatory cell makeup [specifically, lymphocyte PD-1 occupancy, myeloid-derived suppressor cells (MDSC), regulatory T cells (Treg), CD4 and CD8 T Cells, TCR repertoire] at the start of treatment, during the intermittent phase and off treatment

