4.1 Inclusion Criteria

Patients must meet all the following criteria to be eligible for study enrollment.

- Men and women ≥ 18 years of age.

- Histological confirmation of urothelial carcinoma (any histology)
- Advanced or metastatic urothelial carcinoma.
- Has received at least 20 weeks on CPI therapy per standard of care (SOC) for advanced urothelial carcinoma
- Karnofsky Performance Score (KPS) $\geq 70\%$ (for more information on KPS, please see: http://www.npcrc.org/files/news/karnofsky_performance_scale.pdf)
- Willing and able to provide informed consent.
- Laboratory criteria for study entry must meet the following criteria:
 - Serum creatinine $\leq 2 \times$ ULN OR CrCl $\geq 30 \text{ mL/min}$ (measured or calculated using the Cockcroft-Gault formula).
 - Hb $\geq 8.0 \text{ g/dL}$
 - AST and ALT $\leq 3.0 \times$ ULN
 - Bilirubin $\leq 1.5 \times$ ULN (except subjects with Gilbert Syndrome, who can have total bilirubin $< 3.0 \text{ mg/dL}$)

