11.0 STUDY PARAMETERS AND CALENDAR

	Screening (≤ 4 weeks prior to dosing)	Cycle 1 Day1 (+/- 3 days) ¹ *	Cycle 2+ D1 (+/- 2 or 3 days) for patients on therapy and for patients re- starting therapy ^{2*}	Patients OFF therapy: every 6 weeks (+/- 3 days) ¹³	Patients OFF therapy: Every 12 weeks (+/- 3 days) ¹³	End of Treatment (+/- 3 days) ¹⁴	Post Study follow up(+/- 3 days) ¹⁵
Informed Consent	X						
ECOG PS, Weight (screening only), Vital Signs	X	X	X	X	X	X	
History/Physic al ³	X	X	X	X	X	X	
Adverse Events		X	X	X	X	X	X
Hematology ⁴	X	X	X	X	X	X	
Chemistry ⁵	X	X	X	X	X	X	
TSH, T4, T3 ⁶	X		X		X		
Autoimmune labs ⁷	X						
Correlative Studies ⁸	X		X		X		
CPI		X	X				
Tumor Imaging ⁹	X		X		X	As clinically indicated	As clinically indicated
Brain CT or MRI ¹⁰	As clinically indicated		As clinically indicated		X	As clinically indicated	As clinically indicated
Bone Scan ¹¹	As clinically indicated		As clinically indicated		X	As clinically indicated	As clinically indicated
Biopsy ¹²				X			

*One Cycle is 14-28 days. Visit window +/- 3 days for Atezolizumab, Nivolumab, and Pembrolizumab. Visit window is +/- 2 days for Avelumab and Durvalumab.

1. Cycle 1 Day 1 Hematology, chemistry, autoimmune labs, and physical exam need not be repeated if done within 14 days

2. History, physical, AEs, Hematology, Chemistry to be done D1 (+/- 3 days) of every cycle

3. Baseline exam should be comprehensive. Subsequent physical exams can be targeted exams.

4. Hematology: CBC with differential, hemoglobin, hematocrit, platelets
5. Blood chemistry: sodium, potassium, chloride, bicarbonate, BUN, creatinine, albumin, total albumin, bicarbonate, AST, ALT, glucose, LDH (baseline only)
6. TSH, T4, T3: Screening, and on all imaging days, then as clinically indicated.
7. Autoimmune labs ANA by IFA screen, Anti-ENA, Anti-DNA DS, Rheumatoid factor, CCP antibody, ESR, CRP. These only need to be drawn if not drawn prior to initial treatment with CPI therapy.
8. Correlative studies: Correlative studies will be drawn with blood draws at biopsy, screening and prior to each imaging.
9. Tumor imaging: CT of the chest, abdomen, and pelvis (with contrast, if possible) to be performed to assess disease status at screening, and every 12 weeks from Cycle 1 Day 1. Tumor imaging should also be done whenever disease progression is suspected and as clinically indicated.
10. Brain imaging Brain CT or MRI scan to be performed as clinically indicated.

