11. Bone imaging: Bone scan to be performed if clinically indicated.
12. Biopsy is recommended at any time during cycle 1 (for PR and SD patients) and within 3 weeks of any other time period at which a PD or PR is achieved in any patient (unless not feasible or unsafe per investigator discretion. Archival tissue up to 6 months prior to enrollment is acceptable in lieu of a cycle 1 biopsy
13. OFF treatment Patients will be seen every 12 weeks. The 6-week interim visit between scans will be done if clinically indicated. Labs during the 6-week interim visit should be as clinically indicated.
14. End of treatment: End of treatment visit is defined as the visit during which the patient will be removed from the study (even if not receiving drug at that visit).
15. Post- study follow up Patients will continue to be followed for at least 30 days after the last dose of CPI therapy or until new anti-cancer treatment is initiated, whichever comes first. Phone follow-up is sufficient.

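### If criterion 4.1 governs entry, no blood is scheduled before checkpoint inhibitor (CPI) therapy, and the archival tissue limit, counted from enrollment, admits at most about 6 weeks of pre-CPI tissue

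*Combined protocol and SAP*

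**What the plan says.** Criterion 4.1 reads "Has received at least 20 weeks on CPI therapy per standard of care (SOC) for advanced urothelial carcinoma", with no upper limit, and section 4.0 makes every criterion mandatory.

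- **Blood.** Section 2.3 plans to study immune cells "at the start of treatment, during the intermittent phase and off treatment". Calendar footnote 8 sets the sampling times: "Correlative studies will be drawn with blood draws at biopsy, screening and prior to each imaging".
- **Tissue.** Section 2.3 asks for markers of response and resistance. Section 10.2 says of archival material "A minimum of 3 unstained slides, up to 6 months prior to enrollment are allowed", and calendar footnote 12 says "Archival tissue up to 6 months prior to enrollment is acceptable in lieu of a cycle 1 biopsy". Fresh biopsy in cycle 1 is recommended for patients already classed as PR or SD.
- **Purpose.** Section 1.4 hopes for a marker "to identify patients likely to benefit from CPI will help prospectively select patients for therapy", and separately for markers of who can tolerate long breaks from therapy.

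Other text points to a different order of events. Section 14.1 enrolls at least 50 patients and then describes 20 or more weeks of CPI. Two exclusion windows in section 4.2 count back from the first study dose. The calendar puts screening within 4 weeks before dosing.

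**The concern.** A marker meant to predict response to CPI has to be measured before CPI. Section 1.3 puts typical time to response at about 2 months, with a range of 1.4 to 2.85 months. If patients enter after 20 weeks or more, the first study blood sample comes after the tumor shrinkage it might be asked to predict. A result reported as a start-of-treatment value would be mislabelled.

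Tissue has a similar problem. The archival limit is counted from enrollment rather than from the first CPI dose, so most of the look-back falls on treatment. Archival tissue may replace a cycle 1 biopsy that under 4.1 is itself on-treatment, and section 10.2 does not ask for the two kinds to be told apart. In gene-expression work, CPI exposure would then be confounded with markers of response or resistance.

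**Working it through.** The documents give no sample size, rate or precision for the correlatives, so there is no planned figure to reproduce. The check is date arithmetic.

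**Inputs**
- Minimum CPI exposure at entry: 20 weeks, no maximum (section 4.1).
- Archival look-back: 6 months before enrollment (section 10.2, footnote 12). 365.25 / 2 / 7 = 26.1 weeks.
- Slowest time to response quoted in section 1.3: 2.85 months. At 26.1 / 6 = 4.35 weeks per month, this is 12.4 weeks.

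**Blood.** The earliest scheduled draw is at screening for entry. Under 4.1 this falls at 20 weeks of CPI or later, beyond the 12.4 weeks above. No earlier draw appears in the calendar.

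**Tissue.** Pre-CPI window = max(0, look-back − weeks on CPI at enrollment).

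| Weeks on CPI at enrollment | Window, 6 months = 26.1 weeks | Share of look-back | Window, 6 months read as 24 weeks |
|---|---|---|---|
| 20 | 26.1 − 20 = 6.1 weeks | 23% | 4 weeks |
| 22 | 4.1 weeks | 16% | 2 weeks |
| 24 | 2.1 weeks | 8% | 0 |
| 26.1 or more | 0 | 0% | 0 |

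Even for entry at exactly 20 weeks, 20 / 26.1 = 77% of the look-back lies on CPI.

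**Share of existing pre-CPI tissue excluded.** This needs the age of each patient's tissue at CPI start and the weeks on CPI at entry. The documents give neither. As an illustration only, assume tissue age at CPI start is uniform over 0 to A weeks. The share excluded is then 1 − min(1, window / A).

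| Entry at | A = 8 | A = 12 | A = 26 | A = 52 |
|---|---|---|---|---|
| 20 weeks | 24% | 49% | 77% | 88% |
| 24 weeks | 74% | 83% | 92% | 96% |
| 26.1 weeks or more | 100% | 100% | 100% | 100% |

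The range is too wide to support any single figure.

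**Order of entry and CPI.** Two places besides 4.1 assume that CPI comes first. Footnote 7 says of the autoimmune labs "These only need to be drawn if not drawn prior to initial treatment with CPI therapy", which makes sense only if screening can follow the start of CPI. A cycle 1 biopsy restricted to PR and SD patients needs a response class that exists before or during cycle 1. Against these stand section 14.1, the section 4.2 windows and the calendar's screening column. Nothing in the text reconciles the two orders.

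**The case against.** The strongest objection is that the entry point is not settled. If patients enroll before CPI, as section 14.1 describes, the screening blood is pre-CPI and a 6-month archival limit is ordinary. First-infusion and first-cycle instructions in sections 6.1 and 9 also fit that order, though they may be label text. The section 3.1 schema and section 5.0 (Registration) could not be read in the available text, and either might define enrollment. This stands: the finding is conditional on 4.1. It does not clear the plan, because on that order 4.1 cannot be met at enrollment and the PR and SD restriction on the cycle 1 biopsy loses its sense.

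It can also be said that the tissue objective names no pre-treatment sample, that biopsies near PD or PR serve the resistance question directly, and that blood at entry is a proper baseline for time off therapy, which is what this trial is about. Prospective selection for CPI appears in the background, not in section 2.3. All of this stands and limits the reach of the point. The correlatives are also hypothesis-generating and biopsies only recommended.

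A recency limit on archival tissue has a purpose too. Accepting tissue of any age could bring in specimens that predate platinum therapy in the refractory patients, which would be a new source of confounding. The remedy should therefore keep a limit and move its anchor.

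**Conclusion.** The point holds conditionally and for the correlative objectives only. If 4.1 governs entry, no pre-CPI blood is scheduled, so the first time point of the blood objective cannot be met from study samples. Qualifying pre-CPI tissue is confined to about 6 weeks before the first dose at best, about 2 weeks for entry at 24 weeks, and none from about 26 weeks. These windows rest only on 4.1 and on reading 6 months as 26.1 weeks. The tissue collected around entry would mix pre-CPI and on-CPI samples without distinguishing them.

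Three stronger readings are not supported:
- A reader might infer that no pre-treatment blood can exist. The documents show only that none is scheduled under 4.1, and other passages imply entry before CPI.
- A reader might infer that the limit rejects most pre-CPI tissue. That depends on tissue ages and entry times not given; the illustration runs from 24% to 100%.
- A reader might count the blood gap as none of 20 patients. Twenty is the intermittent-arm target, whereas correlatives are drawn at screening and sections 3.2 and 14.1 allow for 50 to 75 patients.

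The primary endpoint, sample size and stopping rule are unaffected.

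**What to change.** State when enrollment occurs relative to the first CPI dose, and bring 4.1, 4.2, 14.1 and the calendar into line with that statement. If 4.1 stands:

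1. In section 10.2 and footnote 12, also accept archival tissue taken within 6 months before the first CPI dose. The pre-CPI window is then the full 26.1 weeks whatever the exposure at entry.
2. Record every blood and tissue sample as pre-CPI or on-CPI, with any intervening therapy, and analyse the two categories separately.
3. In section 2.3 and the synopsis, replace the first blood time point with *at study entry, after at least 20 weeks of CPI*. Limit blood-marker conclusions to time off therapy, and do not claim prediction of initial response to CPI.

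Moving the tissue anchor does not supply pre-CPI blood. If that is wanted, it needs consent and a draw before the first dose, or access to banked samples.

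The cost of items 1 to 3 is wording, sample labels and some added slide requests, with no new biopsy or visit. The downsides are a narrower blood objective and possibly lower nucleic-acid quality in older blocks.
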